## BACKGROUND

Lateral elbow tendinopathy (LET), also widely known as "tennis elbow", is the most common musculoskeletal disorder of the elbow causing a significant functional decline with increased disability and productivity loss (1-3). The prevalence of LET ranges from 1% to 3% (4, 5), and it is strongly associated with repetitive activities, office occupation, older age, female gender, smoking, shoulder tendinopathy and obesity (6-8). The common diagnostic factor is pain over the lateral humeral epicondyle during palpation and gripping that may radiate distally into the forearm (9). Although the clinical presentation of LET has been well documented, the aetiology remains inconclusive and the underlying pathophysiology is complex (10, 11).

The conservative management is considered to be the first line of treatment with exercise, orthoses, manual therapy, physical therapy modalities, acupuncture and multimodal physiotherapy treatment (9). However, evidence supporting a form of the most effective treatment approach is unclear. Exercise including eccentric, isometric or concentric-eccentric appears to be the most popular treatment approach with or without passive interventions modalities or injections (12, 13). A number of systematic reviews underlined the value of eccentric exercise in the management of LET at short-term follow-up, however, their superiority compared to other active interventions remains inconclusive (11, 14, 15). The effectiveness of traditional training programmes in the management of LET is unclear since only a few studies report their exercise program in ample detail to allow full replication in clinical practice (Bisset et al., 2006; Coombes et al., 2013; Vuvan et al., 2020)

Important exercise properties such as load, dosage, time under tension, rest periods, acceptable pain level, equipment, duration, frequency etc. are critical barriers to provide clinical recommendations for the optimal exercise selection in LET. Evidently, the research evaluation of innovative and well-developed active interventions seems essential to improve evidence-informed clinical practice in the current field.

#### STUDY RATIONALE

During the last few decades, a new type of training using Blood Flow Restriction (BFR) has been suggested as an effective way to increase muscle strength and mass both in healthy and unhealthy individuals (Patterson et al., 2019). Exercise programmes using heavy loads such as 60- 70% of one repetition maximum (1RM) were considered essential to elicit muscle hypertrophy and strength in 6-8 weeks' time (16)However, low load resistance training using 20%–30% 1RM with BFR, has shown significant improvements in power and hypertrophy of skeletal muscles compared to non-BFR load-matched controls. BFR training has its origins on 'Kaatsu training' and uses a pneumatic tourniquet system which applies an external pressure, to the most proximal region of the upper or lower limbs (17). The use of the tourniquet system results in a partial restriction of arterial blood flow to structures distal to the cuff, while the venous return is also substantially blocked (17, 18). Key role in skeletal muscle reaction to BFR training is thought to be the inadequate oxygen supply (hypoxia) (19, 20).

The positive clinical use of BFR training has been well documented in systematic reviews including a range of musculoskeletal conditions such as knee

osteoarthritis, anterior cruciate ligament injury, Achilles tendon ruptures, patella tendinopathy etc. (21, 22). The use of BFR in clinical conditions has given promising results not only for muscle strength and mass but also in pain reduction (18, 21, 23, 24). The use of low load resistance training with BFR in conditions where the presence of pain limits the use of high load resistance exercises can be extremely valuable (25, 26). A study including patients with patellofemoral pain syndrome reported that BFR training had statistically better results compared to non BFR programmes in pain reduction and disability scores even with substantial lower load of exercises at 8 weeks follow-up (23). In the same line, the study by Korakakis et al., (2018) including patients with anterior knee pain showed significantly better results of a low load resistance training BFR programme compared to a non-BFR programme in pain reduction lasting for at least 45-min post- intervention. Similarly, studies including patients with anterior cruciate ligament repair showed that the addition of BFR training was more effective compared to the traditional rehabilitation in muscle changes and pain reduction as well (21, 27). According to the authors knowledge there are no research investigations for the effectiveness of BFR training in upper limb tendinopathies including LET. The use of an optimal exercise programme in patients with LET remains inconclusive and the investigation of this new type of rehabilitation training could be valuable in improving the clinical effectiveness of active treatments.

### STUDY OBJECTIVES

To evaluate the effectiveness of low load resistance exercises with blood flow restriction in increasing strength, reducing pain and improving function compared to usual exercises in patients with lateral elbow tendinopathy.

## STUDY DESIGN

## Sample

Forty-two patients, men and women, 18-50 years old with LET and symptoms for more than 2 weeks. Inclusion criteria: pain provoked by palpation on the lateral epicondyle, Cohen's test, Maudsley test, Mill's test, pain free grip strength. All participants will sign an informed consent form prior their participation to the study. Study approval will be obtained from the Ethics Committee of the University of West Attica. Exclusion criteria: shoulder tendinopathy, cervical radiculopathy, reumatoid arthritis, neurological deficit, radial nerve entrapment, past treatment for the elbow before entering the study, professional athletes, LET of the same side in the last 3 years, serious cardiovascular diseases, venous deficiency, history of heart surgery, cancer history, breast surgery, orthopaedic surgeries during the last 6 months, thrombosis, body mass Index  $\geq$  30, Crohn syndrome, family or personal history of pulmonary embolism

## Procedure

Potential participants will be recruited through public invitations in the University of West Attica, local hospitals, General Practitioners and Orthopaedic surgeons.

Individuals who will respond are going to be examined by a musculoskeletal specialist physiotherapist.

#### Measurements

The primary outcome measures include self-perceived recovery measured using 6point Global Rating of Change (GROC) pain free grip strength pain (PFGS) and functionality. GROC measurement will contain a six point Likert scale describing the change from much worse to totally improved, PFGS will be measured with a Jamar hand dynamometer, pain with 0-10 scale (Numerical rated pain scale) and functional disability with the patient-rated tennis elbow (PRTEE) questionnaire. Secondary outcomes include: Tendon thickness, neovascularity, presence of spurs, calcification and/or tears in the common extensor tendon (lateral epicondyle) measured with diagnostic ultrasound imaging. Also, isometric strength measurements of elbow flexors and extensors will be included using the BioFet force evaluation system (mean of three efforts of the maximum isometric contraction). All measurements will be taken at baseline, 6- and 12-weeks followup.

## Interventions

Participants will be randomized with an appropriate software to either a blood flow restriction exercise programme or a placebo blood flow restriction exercise programme. A concealed allocation will be applied. Assessor, therapists and patients will be blinded. Both groups of patients will be treated with a usual exercise programme in lateral elbow tendinopathy (28). One group will use blood flow restriction and the other group placebo blood flow restriction (cuffs without air

inflated). The exercise programmes will be held in physiotherapy sessions (twice a week) for 6 weeks. Also, all patients will be treated with soft tissue massage, the same appropriate advice and a home exercise programme (written workbook). All patients will fill in a diary for monitoring adherence and co-interventions.

## STATISTICAL ANALYSIS PLAN (SAP)

#### **Demographic and Baseline Characteristics**

All randomized participants will be included in statistical analysis. The following demographic and baseline characteristics will be summarized and statistically analyzed: gender, age, height and weight, smoking habits, type of work, physical activity level, previous episodes of LET, time course of condition, severity of pain, disability scores (PRTEE), pain free grip strength, isometric strength test of elbow flexors and extensors.

#### Sample Size and Randomization

The primary outcome measure for the power calculation is the difference between study groups in the change of PFGS between baseline and 12 weeks follow-up. The MCID of PFGS has been evaluated in a group of patients with LET with an age of 42±9 years and relatively equal distribution of males and females (29). These researchers found PFGS to better discriminate improved from non-improved patients with a threshold of 7kg showing the greatest accuracy. Also, we used prior effect estimates from an RCT (30), which compared different exercise programmes in patients with LET reporting a standard deviation in PFGS 7.1 kgr. We have set alpha=0.05 and beta=0.80 and resulted in n=16.15 per treatment group (31, 32).

By estimating up to 10% losses to follow-up our sample was set at 36 participants (31, 32). Patients will be randomly allocated into the study groups. The principal investigator will be responsible for the random allocation by using an online random allocation software. Participants, therapists and assessor will be blinded to the allocation into the study groups.

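### The protocol gives two unreconciled recruitment targets, 42 and 36, and labels its 80% power as beta = 0.80

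*Protocol*

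**What the plan says.** Two sections of the protocol fix the number of patients.

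- Study Design, Sample, opens with "Forty-two patients, men and women, 18-50 years old with LET and symptoms for more than 2 weeks".
- Statistical Analysis Plan, Sample Size and Randomization, closes its calculation with "By estimating up to 10% losses to follow-up our sample was set at 36 participants".

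The calculation concerns "the difference between study groups in the change of PFGS between baseline and 12 weeks follow-up". It takes "a threshold of 7kg showing the greatest accuracy" from one cited study and an SD from a cited trial "reporting a standard deviation in PFGS 7.1 kgr". The result is given as: "We have set alpha=0.05 and beta=0.80 and resulted in n=16.15 per treatment group".

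No section calls 42 a maximum, a revised target or a margin over 36. None says which number governs recruitment.

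**The concern.** Both numbers stand in current text, and each reads as the planned sample. A team that stopped at 36 and a team that went on to 42 could each cite the protocol. The recruitment target should be fixed before the trial starts, so that nobody has to choose it, or defend the choice, once patients are in.

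The power statement is also wrong as written. Beta is the type II error rate, so beta = 0.80 describes a trial that would miss the target difference four times in five. Anyone who checks the calculation from the stated inputs will fail to reproduce it.

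**Working it through.** **Inputs**, all from Sample Size and Randomization: difference 7 kg, SD 7.1 kg, alpha 0.05, 0.80 written as beta, loss up to 10%. Sidedness and allocation ratio are not stated there. I take the test as two-sided, which the first step supports, and allocation as 1:1, since a single n is given for each group.

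**1. Reproduce the stated n per group.** For two means by the normal approximation:

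n = 2 × [SD × (z₀.₉₇₅ + z_power) / difference]²

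- Two-sided, power 0.80: 2 × [7.1 × (1.960 + 0.842) / 7]² = 16.15. This matches.
- One-sided, power 0.80: 12.72. No match.
- Two-sided, beta 0.80 taken literally (power 0.20): 2 × [7.1 × (1.960 − 0.842) / 7]² = 2.57. No match.

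So the calculation used two-sided alpha 0.05 and power 0.80.

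**2. Reproduce the total.** 16.15 / (1 − 0.10) = 17.94, so 18 per group and 36 in total. This matches. Multiplying instead, 16.15 × 1.1 = 17.77, also gives 18.

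**3. Can the same inputs give 42?** Forty-two means 21 per group. To round up to 21, 16.15 / (1 − loss) must lie above 20 and at or below 21. That requires a loss above 1 − 16.15/20 = 19% and at most 1 − 16.15/21 = 23%. The protocol states up to 10%. The two targets differ by 42 − 36 = 6 patients, and 6/36 = 17%.

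**4. Power under each target.** The normal approximation is Φ{7 / [7.1 × √(1/n₁ + 1/n₂)] − 1.960}. The t-test figure uses the noncentral t distribution with n₁ + n₂ − 2 degrees of freedom. Ten percent of 36 is 3.6, so at most 3 whole patients can be lost within the allowance. Ten percent of 42 is 4.2, so at most 4. Losses are spread as evenly as possible.

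| Randomised | Lost | Remaining per group | Power, normal | Power, t-test |
|---|---|---|---|---|
| 36 | 0 | 18 / 18 | 84.1% | 81.9% |
| 36 | 3 (8.3%) | 16 / 17 | 80.8% | 78.3% |
| 36 | exactly 10%, fractional | 16.2 / 16.2 | 80.1% | 77.5% |
| 42 | 0 | 21 / 21 | 89.2% | 87.6% |
| 42 | 4 (9.5%) | 19 / 19 | 86.0% | 84.1% |

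**The case against.** The strongest reply is that nothing is lost either way. By the protocol's formula both 36 and 42 keep at least 80% power after the stated loss. The beta label is a slip that changes no number, and 42 may simply be a deliberate margin. The first two points stand. The third may be true, but the protocol does not say so, and a reader cannot tell a margin from a leftover figure.

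A reader might go further and infer that 36 falls short of 80% power after its own 10% loss. The protocol does not support that.

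- Rounding once, after inflation, is legitimate. At exactly 10% loss 16.2 per group remain, which is not below 16.15.
- A figure of 77.0% (t-test) or 79.6% (normal) belongs to 16 per group. That means 4 of 36 lost, or 11.1%, which is outside the allowance.
- A t-test does give about 78% at 16/17, some 2 points under 80%. But the protocol used the normal approximation, which is a standard formula, and names no t-test.
- The planned analysis (Primary outcomes) is a mixed model adjusted for the baseline value. This may recover the difference, although the protocol gives no correlation from which to say how much.

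A small-sample remark on the t-test is fair as a note. It is not an error in the 36.

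**Conclusion.** Two statements need correction. The recruitment target is given as both 42 and 36, a gap of 6 patients, and only 36 follows from the stated inputs. The power is written as beta = 0.80 although 16.15 per group arises only with power 0.80, that is, beta 0.20.

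The consequence is an unfixed stopping point for enrolment and a calculation that cannot be checked as written. It is not a demonstrated loss of power: after losses within 10%, the protocol's formula gives 80.8% with 36 randomised and 86.0% with 42.

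This rests on equal allocation, a two-sided test, and taking the 7 kg threshold and the SD of 7.1 kg as the difference and SD for the 12-week change, as the protocol's calculation does. The documents do not show which target is intended, so the sponsor has to say.

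**What to change.** State one target in both sections.

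- **If 36:** keep the derivation in Sample Size and Randomization and change the number in the Sample section.
- **If 42 (21 per group):** keep the Sample section and add to Sample Size and Randomization that 42 exceeds the calculated 36. Give the power as about 86% (normal approximation) or 84% (t-test) at 19 per group, after about 10% loss.

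In either case replace the beta statement with *power 0.80 (beta 0.20), two-sided alpha 0.05*.

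The cost is protocol wording only. No formula, loss assumption, visit or measurement changes. Choosing 42 commits the trial to 6 more patients than the calculation requires, but that number is already in the protocol.

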#### Data Analysis

All randomized study subjects will be analyzed using Intention-to-treat analysis. Moreover, all randomized study subjects completing the trial period (complete cases) will be analyzed using per protocol analysis. For the scope of sensitivity analysis, study subjects with missing data on any of the variables will be excluded from the analysis. Hence, the sensitivity of the results regarding the pattern of missing data will be investigated. Model based multiple imputation will be used for both primary and secondary outcomes.

All outcomes will be presented using descriptive statistics; normally distributed data by the mean and standard deviation (SD) and skewed distributions by the median and interquartile range (IQR). Binary and categorical variables will be presented using counts and percentages. The SPSS software (version 25) will be used for all statistical analysis.

## Primary outcomes

The primary analysis will compare the two interventions on their mean change in PFGS, PRTEE scores, pain reduction. The estimated difference in mean change

from baseline to 6 and 12 weeks and the corresponding 95 % confidence interval (CI) will be presented. We will estimate all continuous outcome measures by using baseline values as covariates in linear mixed models. For GROC logistic regression will be used and the odds ratio (OR) including 95 % Confidence Intervals (CI) will be presented.

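### Four outcomes at up to two visits share primary status with no ranking or success rule, while alpha and power are set for PFGS at 12 weeks alone

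*Protocol*

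**What the plan says.** Three sections of the Protocol bear on which endpoint is primary.

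- **Measurements** gives a list: "The primary outcome measures include self-perceived recovery measured using 6point Global Rating of Change (GROC) pain free grip strength pain (PFGS) and functionality". The next sentence there separates the instruments: a six-point GROC, PFGS by dynamometer, a 0-10 pain scale and the PRTEE. That makes four primary outcomes. On timing: "All measurements will be taken at baseline, 6- and 12-weeks followup".
- **Sample Size and Randomization** picks out one comparison: "The primary outcome measure for the power calculation is the difference between study groups in the change of PFGS". It fixes the visit for this comparison at 12 weeks. The only alpha in the document stands here: "We have set alpha=0.05 and beta=0.80 and resulted in n=16.15 per treatment group".
- **Primary outcomes** (analysis) says: "The primary analysis will compare the two interventions on their mean change in PFGS, PRTEE scores, pain reduction". The differences in mean change are reported "from baseline to 6 and 12 weeks and the corresponding 95 % confidence interval (CI) will be presented". The fourth outcome follows: "For GROC logistic regression will be used and the odds ratio (OR) including 95 % Confidence Intervals (CI) will be presented". The GROC sentence names no visit.

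The document gives no order among the outcomes, no main visit, no multiplicity adjustment, and no statement of whether one or all of the primary outcomes must succeed.

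**The concern.** The sample size section treats one comparison as the primary one, and only for the purpose of the power calculation. The sections that define and analyse the primary outcomes give that comparison no priority over the others. A report that followed the Protocol to the letter could therefore lead with PFGS, pain, PRTEE or GROC, at either visit, and call the result primary. That choice could be made after the data are seen.

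At stake is the meaning of the stated 5% and 80%. Both describe PFGS change to 12 weeks. Neither describes a trial that may be declared positive on the best of several comparisons.

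**Working it through.** **Inputs.** From Sample Size and Randomization: difference 7 kg, SD 7.1 kg, alpha 0.05, power 0.80 (the document writes beta=0.80), 10% losses, total 36. From Measurements and Primary outcomes: four primary outcomes and two follow-up visits. The document gives no correlations between outcomes or visits, so those below are assumptions.

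**1. The plan's own figure.** The normal-approximation formula for two means at two-sided 5% is n per group = 2 × [SD × (z₀.₉₇₅ + z₀.₈₀) / difference]².

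2 × [7.1 × (1.960 + 0.842) / 7]² = 16.15 per group, which matches the Protocol. Allowing for losses, 2 × 16.15 / 0.9 = 35.9, so 36. The sample size thus pays for exactly one comparison at 5%.

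**2. Number of primary comparisons.** PFGS, PRTEE and pain at two visits make 3 × 2 = 6. GROC adds one if a single visit is meant. It adds two if the general measurement schedule applies to it. The total is seven or eight.

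**3. Chance of at least one false positive, independent comparisons at 5% each.** The formula is 1 − 0.95^m.

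- m = 7: 1 − 0.6983 = 30.2%
- m = 8: 1 − 0.6634 = 33.7%

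**4. The same chance with correlated comparisons.** This comes from simulating multivariate normal test statistics, 500,000 draws per setting, with two-sided 5% limits.

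| Assumed common correlation | Eight comparisons | Seven comparisons |
|---|---|---|
| 0.3 | 30.0% | 27.1% |
| 0.5 | 25.1% | 23.0% |
| 0.7 | 19.1% | 17.9% |
| 0.8 | 15.7% | 14.9% |

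With separate correlations between outcomes and between visits (four outcomes, two visits), the results were:

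- 29.8% at 0.3 between outcomes and 0.5 between visits
- 24.8% at 0.5 and 0.7
- 20.8% at 0.7 and 0.7
- 19.6% at 0.7 and 0.8

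**5. One visit only.** Four outcomes at a single visit give 1 − 0.95⁴ = 18.5% if independent, and 15.6% at a common correlation of 0.5.

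**6. Cost of splitting alpha instead.** An equal split over eight gives 0.05 / 8 = 0.00625. By the formula in step 1, PFGS would then need 27 per group before losses. With 18 per group, its power would fall from 84% to 59% (52% by a t-test calculation). The Protocol proposes no such split, and its planned model adjusts for baseline, so these figures only compare the repairs.

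**The case against.** The strongest reply is that the Protocol does not say each comparison is tested at 5%. Primary outcomes promises estimates and 95% confidence intervals. It gives no p-value threshold and no rule that any single success is enough. A reader might infer from the list that the trial's false-positive rate simply is 30% or more. The document does not support that. The rate depends on an any-one-succeeds rule that the Protocol neither states nor excludes. What remains is that nothing in the text prevents that use, and a 95% interval excluding no effect is the same decision as a 5% test.

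A reader might also infer that the trial is powered on one endpoint and analysed on another. That goes too far. PFGS is the first outcome listed in the analysis, and 12 weeks is one of its visits. The gap is narrower: the priority given to that comparison for the power calculation is dropped elsewhere.

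Two further points stand in part. The second GROC visit comes only from the general measurement schedule, hence seven or eight. A separate analysis plan might also allocate alpha. But the section in question is itself headed Statistical Analysis Plan, and the identity of the primary endpoint is something this Protocol already states, in two ways that have not been reconciled.

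**Conclusion.** The point holds as an incomplete and inconsistent designation of the primary endpoint. Under the stated condition, that one favourable interval among the primary comparisons is taken as a positive trial, the false-positive chance is 30% to 34% if the comparisons are independent. At assumed correlations of 0.3 to 0.8 it is roughly 16% to 30% for eight comparisons and 15% to 27% for seven. The size depends on correlations that the document does not give, so these figures are illustrations and not bounds. In every case examined the chance is about three times the intended 5% or more. Because this decides what the trial may claim, it should be settled before the data are seen.

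**What to change.** In both Measurements and Primary outcomes, insert wording such as: *The single primary endpoint is the between-group difference in PFGS change from baseline to 12 weeks, tested at two-sided 5%.* List PFGS at 6 weeks, and GROC, pain and PRTEE at both visits, as secondary outcomes reported with estimates and 95% confidence intervals. PFGS at 12 weeks is the natural choice because it is already powered.

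The Study Objectives name strength, pain and function together. If the sponsor wants pain and function to remain confirmatory, state a fixed order in which they are tested after PFGS at 12 weeks, each at 5% and only if every earlier test succeeds. This also holds the overall error at 5%.

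Either route changes wording only and leaves the sample size as it is. The price is that a positive result on pain, PRTEE or GROC alone can no longer be claimed as the primary result. Under the fixed order, pain and function also lose confirmatory standing if PFGS at 12 weeks fails, and the Protocol gives no power calculation for them.

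### Strength is analysed in absolute units in a mixed-sex sample with adjustment for baseline values only; pre-specifying sex as a covariate would be a cheap, modest gain in precision

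*Protocol*

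**What the plan says.** The Sample section of the protocol enrols both sexes: "Forty-two patients, men and women, 18-50 years old with LET". The baseline list under Demographic and Baseline Characteristics includes sex: "gender, age, height and weight, smoking habits, type of work".

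The trial is sized on PFGS in kilograms, as the section Sample Size and Randomization sets out: "The primary outcome measure for the power calculation is the difference between study groups in the change of PFGS between baseline and 12 weeks follow-up". A responder threshold serves as the effect, "with a threshold of 7kg showing the greatest accuracy", taken from a sample described as having a "relatively equal distribution of males and females". The spread comes from another trial, "reporting a standard deviation in PFGS 7.1 kgr".

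The model is stated once, under Primary outcomes: "We will estimate all continuous outcome measures by using baseline values as covariates in linear mixed models". By its wording it also covers the isometric strength outcomes, which the Secondary Outcomes section compares as mean change. Sex is not mentioned in either analysis section.

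**The concern.** Grip and elbow strength are forces in absolute units, and men and women plausibly differ in them. PFGS is also limited by pain at baseline. A man and a woman with the same baseline PFGS may have different maximal grip, and so different room to recover in kilograms. If so, sex carries information about 12-week PFGS that baseline PFGS does not, and that variation stays in the error term of a model adjusted for baseline alone.

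What is at stake is precision on the outcome the trial is sized on, in a sample of 36 to 42 patients. A practical point goes with it. If the arms turn out visibly unequal in sex, adding the covariate after the data are seen would be post hoc and open to challenge. Naming it now avoids that.

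**Working it through.** **1. The plan's own figure.** The statement is "We have set alpha=0.05 and beta=0.80 and resulted in n=16.15 per treatment group". With a difference of 7 kg, SD 7.1 kg, two-sided alpha 0.05 and the 0.80 read as power: 2 × ((1.960 + 0.842) × 7.1 / 7)² = 16.15 per group. With 10% losses, 2 × 16.15 / 0.9 = 35.9, so 36. Both figures reproduce, and sex plays no part in them.

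**2. Chance imbalance.** Assume half the patients are women and the arms are equal, with no restriction on sex. The number of women in one arm is then hypergeometric.
- 18 per arm (N = 36): the probability that the arms differ by at least 4 women is 0.32, and by at least 6 it is 0.09.
- 21 per arm (N = 42, the figure in the Sample section): the probability of a difference of at least 5 women is 0.22.

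**3. What baseline adjustment leaves.** The documents give no grip values by sex and no correlation between visits, so these are assumptions: within-sex SD s = 7.1 kg at both visits, half women, within-sex correlation r = 0.5, 0.7 or 0.8, and sex gap D0 at baseline and D1 at follow-up.
- Baseline variance: s² + D0²/4. Follow-up variance: s² + D1²/4. Covariance: r·s² + D0·D1/4.
- Slope on baseline: b = covariance / baseline variance.
- Residual variance, baseline only: follow-up variance − covariance² / baseline variance.
- Residual variance, baseline plus sex: s²(1 − r²).
- Sex difference left at equal baseline: D1 − b·D0. Shift from a 4-woman imbalance at 18 per arm: (4/18) × that difference.

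Example with a constant gap of 10 kg and r = 0.5: baseline and follow-up variance 50.41 + 25 = 75.41; covariance 25.2 + 25 = 50.2; b = 0.666. Residual variance is 75.41 − 33.42 = 41.99 without sex and 37.81 with it, a cut of 10.0%. Sex difference left: 10 − 6.66 = 3.34 kg. Shift: 0.74 kg.

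Example with a gap widening from 8 to 12 kg and r = 0.5: baseline variance 66.41; follow-up variance 86.41; covariance 49.2; b = 0.741. Residual variance is 49.95 without sex and 37.81 with it, a cut of about 24%. Sex difference left: 12 − 5.93 = 6.07 kg. Shift: 1.35 kg.

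| Sex gap, baseline → follow-up (kg) | Variance cut, over r = 0.5 to 0.8 | Shift, 4-woman imbalance at 18 per arm (kg) |
|---|---|---|
| 5 → 5 | 1.2-3.5% | 0.20-0.49 |
| 10 → 10 | 3.6-10.0% | 0.30-0.74 |
| 15 → 15 | 5.5-15.0% | 0.32-0.79 |
| 5 → 8 | 15-16% | 0.79-1.09 |
| 7 → 10 | 17-18% | 0.79-1.16 |
| 8 → 12 | 23-25% | 0.95-1.35 |

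**4. Power.** Take 7.1 kg as the residual SD after baseline adjustment, which the protocol does not say. The SD after adding sex is 7.1 × √(1 − cut), and t-test power for 7 kg at 18 per arm is:
- no cut: SD 7.10, power 82%
- 1% cut: SD 7.06, power 82%
- 5% cut: SD 6.92, power 84%
- 10% cut: SD 6.74, power 86%

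Steps 3 and 4 read 7.1 kg differently: as a within-sex SD of level in step 3 and as a residual SD in step 4. They are separate illustrations and should not be chained.

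**The case against.** The strongest reply is that the plan already deals with most of this. The contrast is change, and baseline is a covariate. A sex gap that is the same at both visits cancels from raw change, and most of it is absorbed by the adjustment: at most about 0.8 kg remains in the constant-gap rows above. That stands. The larger figures need a gap that widens as pain resolves, which is plausible for a pain-limited measure but documented nowhere.

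The power gain is also uncertain. If 7.1 kg is an SD of level, baseline adjustment alone at an assumed correlation of 0.5 brings it to 7.1 × √0.75 = 6.15 kg and power at 16 per arm to 88%, without sex. At 21 per arm, power is 88% even with 7.1 kg as the residual SD. For isometric strength the pain-limitation argument is weaker, because the Measurements section describes maximal efforts.

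It could be said that covariate choice belongs in a separate analysis plan. That does not dispose of the point: this protocol carries its own analysis-plan section, which states the covariates for every continuous outcome.

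Two stronger readings are tempting, and the documents do not support them. A reader might infer that allocation ignores sex. The Interventions and Sample Size and Randomization sections only say that software is used; they do not say whether it stratifies. A reader might also infer that a sex imbalance would bias the comparison. Under randomisation it is chance error, which the confidence interval reflects.

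**Conclusion.** The point holds as a low-severity improvement. The stated model leaves out a recorded variable that plausibly predicts strength beyond its baseline value. The residual-variance gain from adding it is about 1-15% with a constant sex gap and 15-25% with a widening one. A 4-woman imbalance at 18 per arm would move the adjusted PFGS difference by about 0.2 to 1.35 kg, roughly 3% to 19% of the 7 kg target (0.2/7 and 1.35/7). All of this rests on assumed sex gaps and correlations, on an even sex mix, and, for the imbalance probability, on allocation that does not balance sex.

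It does not follow that the sample size is wrong or that the planned analysis is invalid. The sample-size figure reproduces and adjustment for baseline is sound.

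**What to change.** Under Primary outcomes, add one sentence: sex will be a fixed covariate, alongside the baseline value of the outcome, in the linear mixed model for PFGS. The same can be done for elbow flexor and extensor isometric strength, with less support. Alternatively, state why baseline alone is judged sufficient.

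The cost is one sentence and one degree of freedom per model. No new data are needed. It should be settled before outcome data are examined by arm.
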